CLINICAL RESEARCH PROTOCOL

PROTOCOL TITLE:	A Prospective, Multicenter, Open-Label, Single-Arm Study of the Safety and Tolerability of a Single, Intravitreal Injection of Human Retinal Progenitor Cells (jCell) in Adult Subjects with Retinitis Pigmentosa (RP)
PROTOCOL NUMBER:	JC-01
SPONSOR:	jCyte, Inc.
IND NUMBER:	016299

ORIGINAL PROTOCOL DATE:	December 12, 2014
Amendment 1 Date:	March 20, 2015
Amendment 2 Date:	April 24, 2015
Amendment 3 Date:	November 3, 2015
Amendment 4 Date:	November 18, 2015
Amendment 5 Date:	April 19, 2016
Amendment 6 Date:	July 7, 2016

Investigator Protocol Agreement

The signature below constitutes that I agree to the following:

- I have reviewed the protocol and the attachments.
- This trial will be conducted according to all stipulations of the protocol, including all statements regarding confidentiality, and according to local legal and regulatory requirements and applicable United States federal regulations and International Conference on Harmonization (ICH) guidelines.
- I agree to periodic site monitoring of case report forms and source documents by the Sponsor or designee and by appropriate regulatory authorities.
- I agree to supply the University of California, Irvine or designee with any information regarding ownership interest and financial ties with the Sponsor for the purpose of complying with regulatory requirements.

Investigator Name (Print)

Investigator Signature

Date

Study Synopsis

NAME OF COMPANY: jCyte, Inc	SUMMARY TABLE	(For national Authority Use Only)
NAME OF FINISHED PRODUCT: jCell	Volume:	
NAME OF ACTIVE INGREDIENT:	Page:	
human retinal progenitor cells	Reference:	

Title of study:

JC-01: A Prospective, Multicenter, Open-Label, Single-Arm Study of the Safety and Tolerability of a Single, Intravitreal Injection of Human Retinal Progenitor Cells (jCell) in Adult Subjects with Retinitis Pigmentosa (RP)

Investigators/Study Centers: [name], University of California, Irvine/Gavin Herbert Eye Institute; [name], Retina-Vitreous Associates Medical Group, Los Angeles CA

Study Period: 2015 -2016

Phase of development: Phase 1/2a

Objectives:

Primary Objective

To assess the safety and tolerability of jCell injection at multiple dose levels in subjects with non-syndromic RP

Secondary Objective

To monitor ocular function over a 12 month period following a single injection of hRPC (jCell) to evaluate the potential therapeutic response in subjects with RP.

Methodology:

This is a prospective, multicenter, open-label, single-arm, Phase I/II trial of human retinal progenitor cells (jCell) for the treatment of retinitis pigmentosa (RP). Study subjects will be screened for eligibility, informed consent obtained, baseline studies of primary and exploratory endpoints performed. Then the subjects will be treated with one of two doses of jCell, with initially enrolled patients receiving the lower dose.

Cohort 1: BCVA no better than 20/200 and no worse than Hand Motions

The first four subjects in Cohort 1 will receive an intravitreal injection of 0.5×10^6 hRPC (50 µL volume) into the eye with the worst visual acuity; only one eye will be injected. Subjects will be monitored closely following injection for 60 minutes prior to being released home on the day of treatment, based on intraocular pressure <30mm Hg and vital signs returned to pre-injection. Patients will be treated with ophthalmic corticosteroid eye drops to minimize any inflammation from injection for up to 14 days (including tapering schedule). There will be a minimum four week interval between the treatment of the first and second subjects in this cohort to confirm no serious injection related AEs have occurred for subject #1 prior to treatment of subject #2. Subsequent cohort 1 subjects at the same dose level will be spaced at least one week apart (subjects 2, 3 and 4). All subjects will receive injection of cells into the eye with the poorest visual acuity. Following at least one week of safety observations for the last study subject at the lower dose level, safety and tolerability data will be reviewed by the DSMB.

Assuming no unexpected safety issues, an additional 4 subjects will be enrolled in Cohort 1 and treated at the second dose level, 1.0×10^6 hRPC. Treatment will be similar to the first four subjects, i.e. intravitreal injection under topical anesthesia with treatment of the first two subjects separated by at least 4 weeks and subsequent subjects in this cohort (subject 6, 7 and 8) spaced at least one week apart. Following at least one week of safety observation for the last Cohort 1 subject, safety and tolerability data will be reviewed by the DSMB prior to initiation of Cohort 2.

Following completion of DSMB review of the first 8 subjects in Cohort 1 (dose levels 0.5×10^6 and 1×10^6 hRPC), an additional three subjects may be enrolled into Cohort 1 and treated at the third dose level, 2×10^6 hRPC (50μ L volume). Treatment will be administered as described above for the first two dose levels, with all subjects spaced at least a week apart. Following at least one week of safety observations for the last study subject at the 2×10^6 hRPC dose level, safety and tolerability data will be reviewed by the DSMB. Assuming no unexpected safety issues and with DSMB recommendation, an additional 3 subjects may be enrolled into Cohort 1 for treatment at the highest dose level, 3.0×10^6 hRPC (50μ L volume). Treatment will be administered as described above for the first two dose levels, with all subjects spaced at least a week apart.

NAME OF COMPANY: jCyte, Inc	SUMMARY TABLE	(For national Authority Use Only)
NAME OF FINISHED PRODUCT:	Volume:	
jCell	Page:	
NAME OF ACTIVE INGREDIENT: human retinal progenitor cells	Reference:	
naman realing progeniter com		

Cohort 2: BCVA no better than 20/40 and no worse than 20/200

The first four subjects in Cohort 2 will receive an intravitreal injection of 0.5×10^6 hRPC into the eye with the worst visual acuity; only one eye will be injected. Subjects will be monitored closely following injection for 60 minutes prior to being released home on the day of treatment, based on intraocular pressure <30mm Hg and vital signs returned to pre-injection. Patients will be treated with with ophthalmic corticosteroid eye drops to minimize any inflammation from injection for up to 14 days (including tapering schedule). Assuming no unexpected safety issues in the low dose group, an additional 4 subjects will be enrolled in Cohort 2 and treated at the second dose level, 1.0×10^6 hRPC.

Once the first two dose levels are completed in Cohort 2, and following the review of safety data from Cohort 1 subjects who were treated at the third dose level (2.0×10^6 hRPC), three additional subjects may be enrolled into Cohort 2 and treated at the 2 x 10⁶ hRPC dose level. Following this and assuming no unexpected safety issues in the Cohort 1 subjects at the 3 x 10⁶ dose level, three additional subjects may be enrolled into Cohort 2 and treated at this highest dose level.

Assuming safety and tolerability data from both dose levels in cohort 1 are acceptable, there will be no minimum interval between treatment of subjects in Cohort 2.

If ≥ 2 patients develop the same CTCAE grade 3 adverse event or 1 patient develops a CTCAE grade 4 adverse event, the study will be suspended until the DSMB reviews the events and makes a determination whether to continue. If a Grade 3 or worse event is clearly attributable to a non-treatment event and therefore not a suspected adverse reaction: [21CFR312.32(a)] the event will not be considered for the purposes of stopping.

Number of patients: up to 28 patients are planned for inclusion, 14 in each vision cohort

Diagnosis and main criteria for inclusion:

Inclusion Criteria

The following conditions must be met before a subject may be enrolled in the study.

- 1. Willing to give written informed consent, able to make the required study visits and follow study protocol instructions.
- 2. Willing to consent to gene mutation typing. Mutation typing will be restricted to typing for eye disease-related genes known to be involved in inherited retinal degenerations and related disorders. If typing results are already available for the subject, the previous results can be recorded and this requirement is waived.
- 3. Clinical diagnosis of RP confirmed by ERG.
- 4. BCVA 20/200 or worse and no worse than HM in cohort 1; and BCVA 20/40 or worse and no worse than 20/200 for the second cohort.
- 5. Male or female, age ≥ 18 yr.
- 6. Adequate organ function:
 - blood counts (hematocrit, Hgb, WBC, platelets and differential) within normal range, or if outside of normal range, not clinically significant as judged by the investigator
 - \circ liver function: alanine transaminase [ALT] and aspartate transaminase [AST] ≤ 2 times the upper limit of the normal range
 - \circ total bilirubin ≤ 1.5 times the upper limit of the normal range
 - \circ renal function: serum creatinine ≤ 1.25 times the upper limit of the normal range
- 7. Negative infectious disease screen (hepatitis B, C or HIV); and drugs of abuse (negative urine screen).
- 8. A female patient of childbearing potential (not surgically sterlized and less than one year postmenopausal) must have a negative pregnancy test (urine human chorionic gonadotropin) at entry (prior to injection) and must have used medically accepted contraception for at least one month prior to treatment. Women of childbearing potential and men must be advised to use a medically accepted method of contraception for at

NAME OF COMPANY: jCyte, Inc	SUMMARY TABLE	(For national Authority Use Only)
NAME OF FINISHED PRODUCT:	Volume:	
jCell	Page:	
NAME OF ACTIVE INGREDIENT: human retinal progenitor cells	Reference:	

least 12 months following treatment.

9. Willing to provide a blood sample for HLA typing, if not done previously with available results

Exclusion Criteria

Patients will be excluded from this study if they meet any of the following criteria:

- 1. Eye disease other than RP that impairs visual function (including retinal vascular disease, elevated intraocular pressure/glaucoma, severe posterior uveitis, clinically significant macular edema), or media opacity precluding visual exam, as well as patients who require other intravitreal therapies
- 2. Pseudo-RP, cancer-associated retinopathies (CAR, MAR) excluded as part of differential diagnosis
- 3. History of malignancy, end-stage major organ disease (heart failure, significant arrhythmias, stroke or transient ischemic attacks, diabetes, immunosuppressive or autoimmune state, major psychiatric disorder, epilepsy, thyroid disease, COPD, renal failure, or any chronic systemic disease requiring continuous treatment with systemic steroids, anticoagulants or immunosuppressive agents.
- 4. Known allergy to penicillin or streptomycin.
- 5. Known allergy to or history of adverse reaction to fluorescein.
- 6. History of adverse reaction to DMSO.
- 7. Unable or unwilling to undergo genetic testing, pupil dilation, topical anesthesia or any protocol-required procedure.
- 8. Women who are nursing or who are planning to nurse during the 12 months that would follow study treatment.
- 9. Any circumstance that in the opinion of the investigator, would interfere with participation in, or compliance with the study protocol
- 10. Treatment with corticosteroids (systemic, periocular or intravitreal) or any other non-approved, experimental, investigational or neuroprotectant therapy (systemic, topical, intravitreal) in either eye within 90 days of study enrollment
- 11. Cataract surgery within three months prior to enrollment or anticipated to need cataract surgery within a year of treatment
- **12.** Participation in a clinical trial for eye disease within 6 months.

Test product, dose and mode of administration:

The investigational product (jCell) is a live suspension of $0.5-3.0 \times 10^6$ human retinal progenitor cells (hRPC) suspended in clinical grade medium. The hRPC are of allogeneic human fetal origin. Study subjects will receive a single dose of either 0.5, 1.0, 2.0, 3.0 x 10^6 jCell as an intravitreal injection under topical anesthesia into the eye with the worst visual acuity.

Duration of treatment:

Treatment with jCell consists of a single intravitreal injection. The injection procedure itself takes approximately 2 minutes. Patients will be released to home on the day of injection. Study subjects will be followed for one year post-injection under this protocol with a separate protocol planned for two additional years of long term follow up.

Criteria for Evaluation:

Efficacy:

Efficacy will be assessed based on a series of ophthmalogic assessments at specified timepoints, including best corrected visual acuity (BCVA), spectral domain optical coherence tomography (OCT), electroretinogram (ECG), visual field testing (where appropriate), fluorescein angiography, autofluorescence and a visual quality of life

NAME OF COMPANY: jCyte, Inc	SUMMARY TABLE	(For national Authority Use Only)
NAME OF FINISHED PRODUCT: iCell	Volume:	
NAME OF ACTIVE INGREDIENT:	Page:	
human retinal progenitor cells	Reference:	

questionaire (VFQ-25). In addition, several low vision assessment tools may be explored in subsets of subjects in order to better understand which assessments may be most useful for this type of treatment approach. None of these assessments are invasive.

Safety:

Safety will be assessed on an ongoing basis by adverse events, identification of dose-limiting toxicities (if any), physical examinations and vital signs, clinical laboratory values, and anti-drug antibodies. In addition, specific ophthalmalogic tests to monitor safety will be performed, including slit lamp and fundus examiniation, B-scans and intraocular pressure (IOP). Additional ophthalmalogic tests described above will also contribute to safety monitoring.

Clinical safety data will be reviewed on an ongoing basis. Safety data will undergo formal review by a DSMB following completion of each dose level 1 in Cohort 1 before initiation of the next dose level in Cohort 1, and before the initiation of the same dose level in Cohorty 2.

Statistical methods:

Background and demograhic data will be summarized for all subjects using descriptive statistics.

Efficacy:

Since this is an exploratory study, no formal hypothesis testing will be done. Descriptive statistics will be used to tabulate and summarize study outcomes. The baseline results of clinical examinations of the injected eye serve as controls for the injected eye. Results of testing of the non-tested eye will also be described. Continuous variables will be summarized descriptively (sample size, mean standard deviation and error, minimum and maximum). Discrete variables will be summarized by frequency or percentage, and analyzed with non-parametric statistics.

Safety:

The safety analyses of AEs and laboratory parameters will include descriptive statistics. Summaries of AEs will be generated by type (AE or SAE), body system and preferred term, severity, and relationship to study product.

TABLE OF CONTENTS

1.0	INT	RODUCTION1	10
1.1	BA	ckground	
1.	1.1	Retinitis Pigmentosa 10	
1.	1.2	Stem /Progenitor Cells	
1.	1.3	CNS and Retinal Progenitor Cells11	
1.2	JCE	ELL (HUMAN RETINAL PROGENITOR CELLS, HRPC)12	
1.3	RA	TIONALE FOR THE PROPOSED STUDY	
2.0	OBJ	ECTIVES 1	14
2.1	Pri	MARY OBJECTIVE	
2.2	SEC	CONDARY OBJECTIVES	
3.0	STU	DY DESIGN1	14
3.1	STU	JDY POPULATION	
3.	1.1	Cohort One	
3.	1.2	Cohort Two 16	
3.2	En	DPOINTS	
3.2	2.1	Efficacy Endpoints	
3.2	2.2	Safety Endpoints 17	
3.3	STU	JDY DURATION	
3.4	EA	rly Study Termination	
4.0	SUB	JECT SELECTION 1	18
4.1	Inc	CLUSION CRITERIA	
4.2	Exe	clusion Criteria	
4.3	Su	BJECT WITHDRAWAL CRITERIA	
4.4	Dis	SCONTINUATION/WITHDRAWAL PROCEDURES	
5.0	SUB	JECT REGISTRATION	20
6.0	TRE	ATMENT PLAN	21
6.1	Do	se and Schedule	
CONF	FIDEN	TIAL 7 of 41	

6.2		TREATMENT COMPLIANCE			
6.3		SUP	UPPORTIVE CARE/PROHIBITED TREATMENTS		
7.0	S	TUI	DY EVALUATIONS		
7.1		SCR	EENING		
7.2		Bas	ELINE (SHOULD BE WITHIN 30 DAYS OF TREATMENT)		
7.3		BEF	ORE ADMINISTRATION OF JCELL (DAY 0)	24	
7.4		Aft	FER ADMINISTRATION OF A SINGLE INTRAVITREAL DOSE OF JCELL (DAY ())24	
7.5		Fol	LOW UP VISITS	25	
7	.5.1		Day 1 (24 hours)	25	
7	.5.2	2	Day 2 (48 hours)		
7	.5.3	5	Day 7 (week one)	25	
7	.5.4	ļ	Day 14 (week two) +/- 1 day		
7	.5.5	5	Day 21 (week three) +/- 1 day		
7	.5.6)	Day 28 (week four/month 1) +/- 1 day		
7	.5.7	7	Month 2 (Day 60) +/- 4 days		
7	.5.8	8	Month 3 (Day 90) +/- 4 days		
7	.5.9)	Month 4 (Day 120) +/- 4 days		
7	.5.1	0	Month 5 (Day 150) +/- 4 days		
7	.5.1	1	Month 6 (Day 180) +/- 4 days		
7	.5.1	2	Month 9 (Day 270) +/- 4 days		
7.6		End	O OF TREATMENT (MONTH 12) OR EARLY TERMINATION VISIT		
8.0	A	SSE	ESSMENTS		
8.1		SAF	ETY ASSESSMENTS		

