3.1 Study Population

3.1.1 Cohort One

Up to 14 subjects will be enrolled into Cohort 1. Subjects in Cohort 1 must have BCVA no better than 20/200 and no worse than Hand Motions (HM, i.e. the patient can distinguish horizontal from vertical hand motions at 1 foot). The first four subjects in Cohort 1 will receive an intravitreal injection of 0.5 x 10^6 hRPC (50 μ L volume) into the eye with the worst visual acuity; only one eye will be injected. The procedure does not require in-patient hospitalization and can be done under topical anesthesia. Subjects will be monitored closely following injection for 60 minutes prior to being released home on the day of treatment, based on intraocular pressure <30mm Hg and vital signs returned to pre-injection. Patients will be treated with ophthalmic corticosteroid eye drops to minimize any inflammation from injection for up to 14 days (including tapering schedule). There will be a minimum four week interval between the treatment of the first and second subjects in this cohort, with follow up at 1, 2, 3, 7, 14 and 21 days post-injection by the study investigator to confirm no serious injection related AEs have occurred for subject #1 prior to treatment of subject #2. Subsequent cohort 1 subjects at the same dose level will be spaced at least one week apart (subjects 2, 3 and 4), with follow up at 1, 2 and 3 days post-injection for each subject prior to treatment of the next subject at that dose level. All subjects will receive injection of cells into the eye with the poorest visual acuity. Following at least one week of safety observations for the last study subject at the lower dose level, safety and tolerability data will be reviewed by the DSMB. Assuming no unexpected safety issues and with DSMB recommendation, an additional 4 subjects will be enrolled in Cohort 1 and treated at the second dose level, 1.0 x 10⁶ hRPC. Treatment will be similar to the first four subjects, i.e. intravitreal injection under topical anesthesia with treatment of the first two subjects separated by at least 4 weeks and subsequent subjects in this cohort (subject 6, 7 and 8) spaced at least one week apart. Following at least one week of safety observation for the last Cohort 1 subject, safety and tolerability data will be reviewed by the DSMB prior to initiation of Cohort 2.

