3.2.2 Safety Endpoints

The primary goal of the study is to evaluate the safety and tolerability of jCell injection: The criteria that will be used to establish safety include:

- Slit-lamp findings, i.e., anterior chamber cell or flare; acute cataract development or progression in phakic patients, vitreous haze.
- Absence of tumor formation, overt immune rejection, decrease in BCVA attributable to treatment
- Absence of clinically significant, persistent increase in intraocular pressure (>10 mm Hg above baseline or IOP > 25 mm Hg), clinically significant epiretinal membrane, retinal detachment, neovascularization, or endophthalmitis
- No clinically significant adverse events attributable to investigational product (jCell) injection
- Patient comfort (no intolerable pain related to procedure)

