If ≥ 2 subjects develop the same CTCAE grade 3 adverse events or 1 subject develops a CTCAE grade 4 adverse events, the study will be suspended until the DSMB reviews the events and makes a determination whether to continue. If a Grade 3 or worse event is clearly attributable to a non-treatment event and therefore not a suspected adverse reaction, the event will not be considered for the purposes of stopping.

The schedule of observations and assessments during the study are summarized in Table 2 of the study protocol.

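### The DSMB suspension rule counts CTCAE grades only and is not tied to the harms in protocol 3.2.2, so a first such harm, unless graded 4, need not reach the DSMB before the next injection within a dose level

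*Protocol*

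**What the plan says.** **The suspension rule.** The synopsis (Methodology) gives the trigger as "If ≥ 2 patients develop the same CTCAE grade 3 adverse event or 1 patient develops a CTCAE grade 4 adverse event"; in that case "the study will be suspended until the DSMB reviews the events and makes a determination whether to continue". SAP section 3 repeats it: "If ≥ 2 subjects develop the same CTCAE grade 3 adverse events or 1 subject develops a CTCAE grade 4 adverse events". The next sentence of the synopsis removes events not caused by treatment, in different terms: "If a Grade 3 or worse event is clearly attributable to a non-treatment event". Neither version names an ocular event.

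**The safety criteria.** Protocol 3.2.2 lists what will be used to establish safety, which is the primary objective. The list includes "Absence of tumor formation, overt immune rejection, decrease in BCVA attributable to treatment" and, along with persistent pressure rise, the absence of "clinically significant epiretinal membrane, retinal detachment, neovascularization, or endophthalmitis".

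**Scheduled DSMB review.** The synopsis (Criteria for Evaluation, Safety) and 3.1.1 place formal review after each Cohort 1 dose level, before the next Cohort 1 level and before Cohort 2 starts the same level. No review of Cohort 2's own data is scheduled. Section 3.1.2 sets no minimum spacing in Cohort 2, provided that Cohort 1 data at the relevant dose are acceptable.

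**Severity as recorded.** Protocol 9.1 records intensity on a five-word scale from mild to death. SAP 10.2 tabulates mild to life-threatening. Neither section records a CTCAE grade.

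**The concern.** The list of harms that define safety and the rule that sends events to the DSMB are written in different terms, and nothing connects them. Most of the 3.2.2 criteria are stated as the absence of something, so a single occurrence already bears on the primary objective. The rule does not react to a single occurrence unless it is graded 4.

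This is a small escalation study of a live-cell injection, and the protocol's prior human data come from three patients (section 1.3). What is at stake is independent review of a first serious eye event before another subject receives the product.

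**Working it through.** **1. The plan's own figure.** Each cohort has levels of 4, 4, 3 and 3 subjects (3.1.1 and 3.1.2; for the second level, "an additional 4 subjects will be enrolled in Cohort 1 and treated at the second dose level"). 4 + 4 + 3 + 3 = 14, and 2 × 14 = 28, which matches "up to 28 patients are planned for inclusion, 14 in each vision cohort". SAP section 4 says the sample size has no formal statistical basis. The documents state no event rate, toxicity limit or operating characteristic for the rule.

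**2. What the rule does with each kind of event, as written.**

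| Event in treated eyes | Suspension rule met? |
|---|---|
| One 3.2.2 harm, grade 1 to 3 | No |
| Two subjects, two different grade 3 harms | No, not the same event |
| Two subjects, same grade 3 harm | Yes |
| One harm graded 4 | Yes |
| One fatal event | Not literally named; the following sentence covers grade 3 and above |
| Faster ERG and BCVA decline in one subject | Not mentioned; 8.2.2 halts enrollment |

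**3. Other routes an event could take.**

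- Cohort 1, subject 1 to subject 2 (3.1.1): at least four weeks, with the investigator confirming no serious injection-related event. DSMB not named.
- Later Cohort 1 subjects (3.1.1): at least one week apart; for subjects 2 to 4, follow-up on days 1 to 3 before the next injection. DSMB not named.
- Second level in Cohort 2 (3.1.2): conditional on no unexpected safety problem at the low dose. DSMB not named for that judgment.
- Serious events (9.2, 11.1): telephoned at once to the sponsor or designee. DSMB not named.
- Single-patient enrollment halt (8.2.2): no numerical threshold, no DSMB step.
- Ongoing review of safety data (synopsis): the reviewer is not named.

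No route sends a first 3.2.2 harm of grade 3 or lower to the DSMB between scheduled reviews.

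**4. Size, with assumed rates.** Let p be an assumed probability per subject of one specific harm at grade 3, equal and independent across n subjects.

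- At least one case: 1 − (1 − p)^n
- Rule met (two or more cases): 1 − (1 − p)^n − n·p·(1 − p)^(n−1)

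For n = 28 and p = 0.05: no case 0.238, exactly one 0.350. At least one is 0.762, and two or more is 0.412.

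| n | p | At least one case | Rule met |
|---|---|---|---|
| 3 (one level) | 10% | 27.1% | 2.8% |
| 4 (one level) | 5% | 18.5% | 1.4% |
| 4 (one level) | 10% | 34.4% | 5.2% |
| 4 (one level) | 20% | 59.0% | 18.1% |
| 14 (one cohort) | 5% | 51.2% | 15.3% |
| 28 (study) | 2% | 43.2% | 10.7% |
| 28 (study) | 5% | 76.2% | 41.2% |
| 28 (study) | 10% | 94.8% | 78.5% |

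The rule counts patients across the study, so the level and cohort rows apply when no case has occurred elsewhere.

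**5. Effect of requiring the same event.** Assume four independent harms at 2.5% each, all grade 3, in 14 subjects. There are 4 × 14 = 56 opportunities.

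- Any harm: 1 − 0.975^56 = 75.8%.
- Two or more harms of any kind (possibly in one subject): 41.0%.
- Rule met, the same harm in two subjects: 17.4%.

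**6. The severity scale.** If the five recorded words are mapped to grades 1 to 5 (an assumption; the documents give no mapping), an eye event that threatens sight but not life reaches at most grade 3. A first case would then never meet the rule.

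**The case against.** The strongest reply is that 3.2.2 defines endpoints and the synopsis paragraph defines a suspension rule. They serve different purposes and need not match. That is fair: this is a gap between two parts of the plan, not a formal contradiction.

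The second reply is that other safeguards apply, and they do. In Cohort 1, an event seen before its level's review leaves at most three further subjects (two in the 3-subject levels), at least a week apart, before the DSMB meets. Cohort 2 opens at a dose only after Cohort 1 data at that dose have been reviewed. The sponsor may suspend at any time (4.3).

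Some stronger readings are tempting and are not supported:

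- *That the grade count is the only written trigger for a pause.* Section 8.2.2 contains a single-patient enrollment halt, and treatment-related BCVA loss is itself a 3.2.2 criterion.
- *That a first detachment, endophthalmitis or tumor cannot suspend the study.* One graded 4 does so at once. The documents give neither the CTCAE version nor a grade for any named harm.
- *That the DSMB would never learn of a single case.* With 28 subjects at 5%, 46% of trials with any case have exactly one (0.350 / 0.762). That means the grade 3 rule is unmet, not that the DSMB is unaware; Cohort 1 data are reviewed after each level.
- *That at a 10% rate the second case comes at about subject 20.* 2/p = 20 assumes unlimited enrollment. Within 28 subjects, a second case occurs in 78.5% of trials.
- *That fatal events are meant to be excluded.* The adjoining sentence suggests otherwise, and deaths are reported to the sponsor immediately. This is a wording mismatch.

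What remains is that none of these safeguards sends a first such event, at grade 3 or lower, to the DSMB between scheduled reviews.

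**Conclusion.** The point holds as a statement about what the plan does not require, and it should be corrected. The textual finding does not depend on any assumed rate. The gap is widest in Cohort 2, where up to 14 subjects may be treated without minimum spacing and without scheduled DSMB review of their own data.

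The percentages are illustrations only. They assume one constant rate per subject, independence, and that every case is graded exactly 3; a rate that changes with dose would alter them. DSMB operating procedures are not among the documents and might already require notification. If so, the protocol should say so.

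**What to change.** Reconcile the synopsis suspension paragraph, protocol 3.2.2, 8.2.2 and 9.1, and SAP section 3. The suspension paragraph and its SAP copy should state how four things relate to the rule: the 3.2.2 criteria, the enrollment halt in 8.2.2, the severity scale actually recorded, and fatal events.

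Add one sentence saying that the sponsor passes a first reported 3.2.2 safety event in a treated eye, in either cohort, to the existing DSMB. Which events count, whether dosing pauses and at what threshold remain decisions for the sponsor and the DSMB; nothing here proposes one.

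The cost is a short protocol edit and the matching SAP text, using the DSMB and event reporting already in place. The downside is an occasional extra DSMB notification. If dosing is already complete, the wording can no longer change conduct, although the gap in the plan remains.
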